## MEASUREMENTS

Assessment will occur at the following time points:

- A. Baseline study visit:
  - a. In person: baseline survey, basic physical measurements (weight, height, waist circumference, and blood pressure).
  - b. Remote visit: baseline survey, basic physical measurements (weight and waste circumference) via telephone/video, height and blood pressure results through chart review
- B. Follow-up study visits at 6 and 12 months:
  - a. In person visit: Follow-up in-person questionnaire and basic physical measurements (weight, waist circumference, blood pressure).
  - b. Remote visit: Follow-up questionnaire, basic physical measurements (weight and waist circumference) via telephone/video, blood pressure results through chart review
- C. Follow-up telephone calls (only patients in PAL intervention): Follow-up telephone questionnaire
- D. Chart review: This will occur periodically to assess MOVE! attendance, PACT teamlet visits (documentation of weight management-related conversations), and medical co-morbidities. Outcomes will be assessed through chart review up to 2 years after the baseline visit.

Baseline Data: Prior to the intervention, patients will receive a Baseline survey. To evaluate recruitment for the intervention, baseline data including socio-demographic information, perceived health status, health literacy, perceived environmental factors, and depression will be collected. Co-morbidities will be determined through chart review of the electronic medical record. We will also collect health-related attitudes, beliefs, and baseline behaviors.

Weight & Height: In person visit, study personnel will obtain patient weight measurements using a standardized protocol which includes; 1) weighing without shoes or heavy garments using a digital scale that will be calibrated monthly; at each study time point (Baseline, 6, and 12 months). 2) Height will be measured using the primary care clinic stadiometer and rounded up to the nearest half-centimeter at Baseline. For remote visits, study personnel will obtain Veteran weight measurements via telephone/video using a standardized protocol which includes: 1) weighing without shoes or heavy garments using a digital scale; 2) at each study time point (Baseline, 6, and 12 months). Height will be obtained through chart review.

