Statistics Analysis: First, all the variables will be summarized using mean with standard deviation and median with interquartile range for continuous variables and frequency table for categorical variables, overall and by randomized arms, respectively. Mann-Whitney tests for continuous variables and Fisher exact tests for categorical variables will be used to check if baseline characteristics are balanced between two arms. Second, Mann-Whitney tests for continuous outcomes and Fisher exact tests for categorical outcomes will be used to compare outcome variables (including intermediate outcomes, behavioral outcomes, and weight outcomes) between two arms at 6 months and 12 months, respectively. Wilcoxon rank tests for continuous outcomes and McNemar tests for binary outcomes will be used to compare them between follow-ups and baseline within each arm. Third, repeated measures modeling based on mixed models will be conducted to compare outcome variables between two arms, utilizing all the data at baseline and three follow-ups. Such modeling can adjust for baseline characteristics, take into account the correlation among repeated measures within subjects, and deal with missing data automatically assuming missing at random. Finally, we will conduct sensitivity analysis based on multiple imputation procedures to examine the impacts of missing data under some missing not at random assumptions.

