We will conduct several statistical analyses to describe Veterans participating in the study. Descriptive statistics, including numerical summaries, frequency tables and graphical displays, will be used to present baseline participant characteristics. Exploratory tests, such as chi-square tests and t-tests, will be used to investigate if baseline characteristics are balanced between two randomized arms. Analysis of missing data due to dropout or incomplete surveys will be investigated by inferring a relationship between baseline characteristics/risk factors and 0-1 indicator that defines whether or not a measurement is observed. This analysis will help to identify factors that are likely to be associated with dropout. Additionally, we will investigate whether the dropout rates are different between two arms. For instance, participants with higher levels of motivation may be more likely to be retained in the study. To deal with these missing, we will incorporate the multiple imputation procedure with the regression analyses to be discussed in the following, along with some sensitivity analysis.

In order to assess the impact of neighborhood-level covariates that may help predict weight loss and behavior change, as well as to better understand and report the environmental context of our study participants, we will determine the Veteran's census tracts and block groups. To do this, we will send a csv file containing the patients' addresses to the VA's geocoding service, Geospatial Service Support Center (GSSC), which uses VA's secured proprietary Enterprise Geographic Information System (GIS) software (<https://www.va.gov/oei/docs/va-spatial-data-strategy.pdf>), via the VA's encrypted email. The data will not include the patient's name or apartment number. GSSC will process the data and return a copy of the spreadsheet with the census tract and block group codes added. Once the data is geocoded, the addresses will be purged from the GSSC's database. All applications of geospatial data will be compliant with the objectives and standards established under the VA Spatial Data Strategy (2022).

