### 1. Test the impact of the PAL intervention on weight change, clinical, and behavioral outcomes

1a: Veterans in the PAL Intervention arm will lose 2.2 kg and 27% will achieve  $\geq 5\%$  weight loss after 12 months of treatment. There will be 0kg weight change in the Enhanced Usual Care arm, and 12% will achieve  $\geq 5\%$  weight loss.

1b: The PAL Intervention will result in improvements in behavioral outcomes (e.g., increased number of steps, increased fruit/vegetable intake, increased attendance to MOVE!) and clinical outcomes (blood pressure, Low Density Lipoprotein (LDL), Hemoglobin A1C, and waist circumference).

1c: The PAL Intervention will increase attendance to MOVE! and/or other intensive programs.

Method: The primary outcome is mean weight loss at 12 months. Mann-Whitney tests for continuous outcomes (e.g., weight loss) and Fisher's exact tests for categorical outcomes (e.g., whether or not Veterans achieve  $\geq 5\%$  weight loss) will be used to compare the two intervention arms at 12 months, respectively. Unadjusted confidence intervals will be computed to measure the effects of the PAL intervention on the outcomes compared with the Enhanced Usual Care. Repeated measures modeling based on mixed models will be conducted to compare outcome variables between intervention arms, utilizing all of the data at Baseline and at follow-up visits. Such modeling can adjust for baseline characteristics (e.g., diabetes, gender), taking into account: a) the correlation among Veterans within providers, b) the correlation among repeated measures within Veterans. Model-based adjusted confidence intervals will be provided to measure the effects of the intervention on the outcomes as well. Although repeated measures modeling can address missing data automatically, assuming it is missing at random, we will use a multiple imputation procedure to conduct sensitivity analyses under the practical assumption of missing not at random. The sensitivity analyses will be conducted using pattern-mixture models to examine if the statistical findings are robust when considering several scenarios, including the least-favorable scenario where the missing data from the PAL intervention arm were to follow the same pattern as that of the observed data from the Enhanced Usual Care arm.

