### 3. Determine the impact of the PAL Intervention on provider and nurse obesity-related counseling practices and attitudes

3a: Veterans in the PAL intervention arm will receive more frequent and higher quality weight management counseling from PCPs than those in the control arm. The intervention will improve PCP self-efficacy, attitudes, and perceived competency in weight management counseling.

Method: Mann-Whitney tests for continuous provider-level outcomes and Fisher's exact tests for categorical provider-level outcomes will be used to compare the two intervention arms at each survey. Confidence intervals of the effects will be computed as well.

Missing Data Analysis (to adjust for response bias) -- Although the repeated measures modeling can address missing data automatically under the assumption of missing-at-random, we will further analyze the missing data due to loss of follow-up or non-response using two popular missing data tools, inverse-probability-weighting approach and multiple-imputations approach. Both missing data approaches utilize the baseline characteristics to adjust for response bias. In addition, we will use multiple-imputations procedure to conduct sensitivity analyses under the practical assumption of missing not at random. Specifically, the sensitivity analyses will be conducted using pattern-mixture models to examine if statistical findings are robust when considering several scenarios, including the least-favorable scenario where missing data from the intervention arm were to follow the same pattern as that of the observed data from the Enhanced Usual Care arm.

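### The missing-data scenario called least-favorable only removes PAL dropouts' benefit and is not a lower bound; the weighting and imputation checks do not name 6-month weight

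*Combined protocol and SAP*

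**What the plan says.** Under Specific Aims Analysis, aim 1, Method, the primary outcome is mean weight loss at 12 months. A repeated-measures mixed model is planned, "utilizing all of the data at Baseline and at follow-up visits", valid under missing at random (MAR). Sensitivity analyses under missing not at random are to use MI with pattern-mixture models over "several scenarios, including the least-favorable scenario where the missing data from the PAL intervention arm were to follow the same pattern" as the observed EUC data. The Missing Data Analysis paragraph after aim 3 repeats this: "several scenarios, including the least-favorable scenario where missing data from the intervention arm were to follow the same pattern". The Statistics Analysis paragraph under Data Analysis adds only that MI will be used "under some missing not at random assumptions".

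On adjustment variables, the Missing Data Analysis paragraph says of IPW and MI: "Both missing data approaches utilize the baseline characteristics to adjust for response bias". It names no post-baseline variable. Weight is measured at baseline, 6 and 12 months (Aim 1: Weight and Clinical Outcomes), and both arms attend the 6-month visit (Study Arms/Randomization).

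On dropout, the Data Analysis section says that "participants with higher levels of motivation may be more likely to be retained in the study" and that "we will investigate whether the dropout rates are different between two arms". Measurements, item C, shows that contact between visits differs by arm: "Follow-up telephone calls (only patients in PAL intervention".

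**The concern.** If missing PAL weights follow observed EUC weights, the treatment benefit among PAL dropouts is zero. The scenario cannot represent dropouts who do worse than controls, for example Veterans who leave because they are regaining weight. A result that survives a scenario with this label may be read as having survived the worst case. The size of any other shift, the rule for missing EUC weights and the variance method are all left open, so they could be settled after the data are seen.

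The second issue concerns the MAR-type checks. If IPW and MI condition on baseline variables alone, they can disagree with the mixed model merely because they ignore 6-month weight. Such a disagreement would be hard to interpret. If early weight change drove dropout differently in the two arms, the checks would be biased where the mixed model is not.

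**Working it through.** **Inputs.** PAL -2.2 kg and EUC 0 kg, with 27% and 12% reaching 5% loss (aim 1a). SD 6.0 kg (Sample Size and Power Analysis). Missing share: the recruitment text gives 75% retention, and the second power paragraph gives 15% missing with 44 evaluable per team. The documents do not reconcile these, so both are used. Two-sided 5% (1.96) is assumed because no level is stated.

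**The plan's own completer count.** 2,615 x 0.20 = 523, and 523 x 0.75 = 392, as stated. For 15%, 52 x 0.85 = 44.2 per team, or 442 over 10 teams.

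**Step 1: is the named scenario a bound?** With missing share m equal in both arms, EUC at 0, and mean change d in missing PAL Veterans, the difference is (1 - m)(-2.2) + m d.

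| d in missing PAL Veterans | m = 0.25 | m = 0.15 |
|---|---|---|
| -2.2 (as observed PAL) | -2.20 | -2.20 |
| 0 (named scenario) | -1.65 | -1.87 |
| +1 | -1.40 | -1.72 |
| +2 | -1.15 | -1.57 |

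The +1 and +2 kg rows are illustrations. For 5% loss at 25% missing, the named rule gives 0.75 x 27 + 0.25 x 12 - 12 = 11.25 points. Counting PAL dropouts alone as non-responders gives 0.75 x 27 - 12 = 8.25 points. The named scenario is the lowest result for neither outcome.

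**Step 2: where would the conclusion tip? (illustration)** SE = 6.0 x sqrt{[1 + (n/k - 1) ICC] x 4/n}, with n evaluable Veterans and k clusters. The PAL-only shift from the MAR estimate that removes significance is (2.2 - 1.96 SE)/m. The plan gives ICC 0.03 to 0.04 for Veterans within team. It is applied here to 10 teams and, as an alternative, to the 17 randomized providers.

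| Missing | Clusters | SE (ICC 0.03, 0.04) | Tipping shift, kg |
|---|---|---|---|
| 25%, n = 392 | 10 | 0.888, 0.964 | 1.8, 1.2 |
| 25%, n = 392 | 17 | 0.781, 0.832 | 2.7, 2.3 |
| 15%, n = 442 | 10 | 0.865, 0.943 | 3.4, 2.3 |
| 15%, n = 442 | 17 | 0.755, 0.807 | 4.8, 4.1 |

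The range is about 1.2 to 4.8 kg. The named scenario is one point in it, a 2.2 kg shift.

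The variance method also matters. With 10 teams, 25% missing and ICC 0.04, the named scenario gives z = 1.65/0.964 = 1.71 if the completer SE is kept. It gives 1.65/(0.75 x 0.964) = 2.28 if the SE shrinks with the estimate.

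**Step 3: IPW and MI without 6-month weight (illustration).** Assume that dropout depends on standardised 6-month change Z in PAL only, with logit P(missing) = a + bZ and a set to give 25% missing. Assume also a 6-to-12-month correlation r of 0.6 to 0.8, b of 0.5 to 1.0, and baseline variables that do not explain Z. None of these values is in the documents. Numerical integration gives E[Z | observed] = -0.120 (b = 0.5) and -0.213 (b = 1.0). The error in the PAL mean is r x 6.0 x E[Z | observed]:
- smallest: 0.6 x 6.0 x (-0.120) = -0.43, so -2.63 kg is estimated;
- largest: 0.8 x 6.0 x (-0.213) = -1.02, so -3.22 kg is estimated.

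The true value is -2.2 kg, so benefit is overstated. With the same mechanism and equal missingness in both arms, the errors cancel and the bias is nil.

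**The case against.** The missing-data plan is already layered: a mixed model under MAR, IPW, MI, pattern-mixture models, a study of what predicts missingness, and a comparison of dropout between arms. The label is defined where it is used, and it could mean only the least favorable of the scenarios planned. The introductory wording is open-ended. All of this stands, and it limits the point to labelling and specification. It does not make the named scenario a bound.

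Four stronger readings are tempting, and the documents do not support them.
- *Harsher scenarios are ruled out.* They are not; they are simply unstated.
- *PAL dropouts are expected to do worse than controls.* The motivation remark concerns dropout in general, and coaching calls confined to PAL show that contact differs, not in which direction outcomes would differ. Equal 2 kg shifts from MAR in both arms, with equal missingness, leave -2.2 kg.
- *The main mixed-model estimate suffers from ignoring 6-month weight.* It does not ignore it.
- *The trial would fail its own scenario.* That turns on the cluster unit, the missing rate and the variance method.

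It is also fair that the text does not say baseline characteristics *only*, and that the bias in step 3 needs an assumed mechanism confined to PAL.

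**Conclusion.** The point holds as a matter of labelling and specification. The scenario is reference-based, and simple alternatives give smaller effects: -1.15 against -1.65 kg at 25% missing, and -1.57 against -1.87 kg at 15%, if PAL dropouts gain 2 kg and EUC is unshifted. These figures rest on the plan's means, equal missingness in the arms, and an illustrative 2 kg.

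The tipping range of about 1.2 to 4.8 kg should be cited only as an illustration, because it moves with the missing rate, the cluster unit, the ICC and the variance method. The 6-month-weight point is secondary in consequence: the MAR mixed-model estimate is unaffected, and the -2.6 to -3.2 kg figures are conditional on assumptions from outside the documents. As written, though, the IPW and MI checks are weaker than the analysis they are meant to support. Priority is minor to moderate.

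**What to change.** 1. State that the IPW and MI models include 6-month weight, where observed, together with baseline characteristics. This helps only for dropouts who attended the 6-month visit.
2. Rename the scenario *reference-based (no benefit in PAL dropouts)*. Add a delta-adjusted tipping-point analysis that starts from the MAR estimate and shifts missing 12-month weights separately by arm over a pre-stated range, for example -2 to +6 kg in 1 kg steps, which covers the illustrative 1.2 to 4.8 kg. Report the combinations at which the 12-month conclusion changes, and state the variance method for each scenario.
3. Reconcile the 15% and 25% missing rates, since the reach of any such analysis depends on them.

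The cost is SAP wording plus a little more programming and output. No new data are needed and the mixed model does not change. The changes should be made before outcome data are examined.

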### 2. Identify predictors of weight loss in Veterans participating in the intervention arm related to intervention components and goal-setting processes

2a: Participation in MOVE!, number of telephone coaching calls received, the use of self-monitoring, and counseling by PACT teams will be associated with weight loss.

2b: Veteran self-efficacy and goal attainment will be associated with weight loss.

Method: Visualization tools such as scatterplots and descriptive analyses such as Spearman correlation coefficients will be used to display associations between weight change and potential predictors. Multivariate regression models will be used to examine the effects of those predictors that are suspected to be associated with weight loss in the intervention arm. Multivariate linear regression models will be considered for continuous outcomes and multiple logistic regression models will be considered for binary outcomes. We will construct classification and regression trees (CARTs), which will generate the variable importance for each intervention component. Missing data will be dealt with using inverse-probability-weighted methods.

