#### Project Methods

To achieve these objectives, we will conduct a cluster randomized controlled trial of 17 PACTs (randomized at the provider level) and 520 of their overweight or obese Veteran patients at the Brooklyn campus of the NY Harbor Healthcare System to study the impact of the 12-month PAL intervention when compared to Enhanced Usual Care. Patients in the PAL intervention will complete the GEM tool and receive health coaching, followed by telephone coaching from the health coach over 12 months. The GEM

tool is a mobile-friendly software program designed to be delivered on tablet computers in the clinic setting to assess lifestyle behaviors and barriers, provide tailored advice and patient education materials, create initial weight loss and behavior change goals, and facilitate counseling by the health coach and PACT staff. Patients in the Enhanced Usual Care arm will receive patient education materials (standard VA Healthy Living Messages) and information on the MOVE! program. All patient participants will attend follow-up visits at 6- and 12-months to assess Body Mass Index, waist circumference, blood pressure, diet, blood tests, physical activity, and goal attainment. PACT staff and health coach outcomes will include 5As-related competency, as well as quality and frequency of counseling. If circumstances restrict the availability of in-person visits (e.g. COVID-19) or based on Veteran's preference, this study will provide a remote/tele-visit option for the baseline and follow up visits.

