Treatment Fidelity: We will do detailed chart reviews using a chart abstraction tool to monitor how often providers see patients and document goal-setting discussions during subsequent visits after the index visit.

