Sample Size and Power Analysis – We base our sample size on within-person weight change at Baseline and 12 months in each arm. We assume an interclass correlation coefficient (ICC) of 0.05 for Veterans within each PCP and an ICC of 0.01 for PCPs within each PACT team. Assuming that at the end of the study we have 5 teams in each intervention arm and recruit and obtain baseline data for 52 Veterans per PACT team (392 Veterans total at 12 months), we will have sufficient power to detect a 2.2kg (SD=6.0kg) difference in weight between the intervention and non-intervention arms. If we do not have PACT attrition (5 PACT teams per arm), then we will have additional power. This amount of weight loss is consistent with findings from the ASPIRE VA study and a systematic review of technology-assisted weight loss interventions in primary care. We will also have the power to detect our hypothesized difference of 15% of PAL Intervention Veterans achieving 5% weight loss (clinically significant—as little as 5% weight loss can improve cardiovascular risk), 85% assuming 12% of intervention arm Veterans achieve this amount of weight loss. We will be able to detect 2.9cm change in waist circumference.

If we assume the missing rate at 12 months is 15%, then we will have 44 evaluable Veterans per team. We assume an interclass correlation coefficient (ICC) of 0.03-0.04 for Veterans within each PACT team and an ICC of 0.01 for PCPs within each team. If the ICC of Veterans within each PACT team is 0.03, the power is 85% to detect a 2.2kg (SD=6.0kg) difference in weight between the intervention and intervention arms; the power is 87% to detect a 2.9cm (SD=7.7cm) difference in waist circumference. This amount of weight loss and waist circumference change is consistent with findings from the ASPIRE VA study and a systematic review of technology-assisted weight loss interventions in primary care. In addition, the power is 91% to detect our hypothesized difference between 25% Veterans in the intervention arm and 10% of Veterans in the control arm achieving 5% weight loss (clinically significant). If the ICC of Veterans within each PACT is 0.04, the powers are 81%, 83%, and 87% to detect the same effect sizes of weight loss, waist circumference, and proportion of 5% weight loss, respectively.

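### Aim 2 names ordinary linear and logistic regression with no term for provider clustering, so standard errors will be too small for any predictor that itself varies between providers

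*Combined protocol and SAP*

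**What the plan says.** Under Statistical and Data Analysis, the Method for Aim 2 covers the intervention arm only. It lists scatterplots, Spearman correlations, regression, classification and regression trees, and inverse-probability weighting for missing data. For the regressions it states "Multivariate linear regression models will be considered for continuous outcomes" and "multiple logistic regression models will be considered for binary outcomes". It mentions no provider effect, GEE or clustered variance, and no variance method to go with the weights.

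Hypothesis 2a reads "Participation in MOVE!, number of telephone coaching calls received, the use of self-monitoring, and counseling by PACT teams will be associated with weight loss". Hypothesis 2b adds self-efficacy and goal attainment.

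The Method for Aim 1, directly before it, says that the mixed model will take into account "the correlation among Veterans within providers". The Sample Size and Power Analysis that closes the document gives two outcome ICCs: "We assume an interclass correlation coefficient (ICC) of 0.05 for Veterans within each PCP" and, in its second paragraph, "We assume an interclass correlation coefficient (ICC) of 0.03-0.04 for Veterans within each PACT team". Project Methods describes 17 PACTs, randomized by provider. The power section works with five teams per arm.

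**The concern.** Ordinary linear and logistic regression treat Veterans as independent. The plan's own ICCs say that Veterans of one provider resemble each other in weight change. If a predictor also differs between providers, the effective sample for its coefficient is smaller than the number of Veterans, and the naive standard error is too small.

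PACT counseling is the predictor most open to this, because it is something the team does. Aim 2 is one of the three study objectives, and its results bear on which components are reported as linked to weight loss. A component could be reported as a predictor on intervals that are too narrow. The primary comparison in Aim 1 is not touched by this point.

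**Working it through.** **Plan's own figure.** The documents state no error rate, power or precision for Aim 2, so there is nothing to reproduce.

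**Inputs from the documents.**
- Clusters in the PAL arm: 17 / 2 = 8.5, so 8 or 9 (Project Methods; equal allocation assumed). Alternatively five (Sample Size and Power Analysis).
- Completers at 12 months: 392 in total, so 392 / 2 = 196 in the PAL arm.
- Completers per cluster, m: 196 / 8.5 = 23.1, or 196 / 5 = 39.2.
- Outcome ICC, ρy: 0.03 to 0.05.

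**Assumptions not in the documents.** Two-sided alpha of 0.05, equal cluster sizes, and the share of a predictor's variance that lies between providers, ρx. No ρx is given for any predictor, so it is varied from 0.05 to 1.

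**Formulas.** For a slope in a linear model that ignores clustering:
- variance inflation V = 1 + (m − 1) × ρx × ρy
- true type I error = 2 × [1 − Φ(1.96 / √V)]

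**Worked cases, m = 23.1.**
- ρx = 0.3, ρy = 0.05: V = 1 + 22.1 × 0.015 = 1.33, √V = 1.15, error 8.9%.
- ρx = 1, ρy = 0.05: V = 1 + 22.1 × 0.05 = 2.10, √V = 1.45, error 17.7%. The naive standard error is 1 / 1.45 = 0.69 of the true one, about 31% too small.
- ρx = 1, ρy = 0.03: V = 1 + 22.1 × 0.03 = 1.66, √V = 1.29, error 12.8%.

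**Results by formula.** Each range runs from ρy = 0.03 to ρy = 0.05.

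| Between-provider share of predictor, ρx | 8–9 providers, m = 23.1 | 5 clusters, m = 39.2 |
|---|---|---|
| 0.05 | 5.4–5.6% | 5.7–6.1% |
| 0.1 | 5.8–6.3% | 6.3–7.2% |
| 0.3 | 7.3–8.9% | 9.1–11.8% |
| 0.5 | 8.9–11.6% | 11.8–16.1% |
| 1 (constant within provider) | 12.8–17.7% | 18.1–25.1% |

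With the 44 evaluable Veterans per team of the second power paragraph, the last cell becomes 19.5–26.9%.

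**Check by simulation** (ordinary least squares, no true effect, 8,000 runs per cell). Eight providers of 24 with ρy = 0.05 reject 5.4%, 5.7%, 8.5%, 10.8% and 18.1% at the five shares in turn. A separate simulation puts the last figure at 19%. With ρy = 0.03 the rates are 5.2%, 5.6%, 6.9%, 8.7% and 13.2%. Five clusters of 39 with ρy = 0.05 reject 5.8%, 7.1%, 10.5%, 13.8% and 25.5%, so the formula runs a little high at intermediate shares when clusters are few.

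**Share needed for a 15% error.** This needs V = 1.854. At m = 23.1 and ρy = 0.05, ρx = 0.854 / (22.1 × 0.05) = 0.77. At ρy = 0.03 the same sum gives 1.29, which is impossible. With five clusters and ρy = 0.05 it is 0.854 / (38.2 × 0.05) = 0.45.

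**Check of remedies** (8 clusters, provider-level predictor). A plain cluster-robust variance with t on 7 degrees of freedom still rejects 13 to 14%. A random intercept with a normal reference rejects 7.8% (clusters of 23, ρy = 0.05).

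**The case against.** The strongest reply is that most Aim 2 predictors belong to the patient: MOVE! attendance, calls received, self-monitoring, self-efficacy and goal attainment. Even PACT counseling is captured patient by patient. The Treatment Fidelity paragraph under Measurements has chart review "monitor how often providers see patients and document goal-setting discussions during subsequent visits after the index visit", and the PACT Team Role paragraph lets the motivational interviewing depend on time and on the Veteran's needs. This stands. A reader might infer that the false-positive rate is about three times nominal across Aim 2. With 8 to 9 providers, that needs a predictor almost identical for all patients of a provider and an ICC near the top of the plan's range. Nothing in the documents shows that any predictor behaves so.

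Second, the plan says that models will be considered, and it rules out no variance estimator. A reader might infer that the sponsor has decided to ignore clustering, but silence does not show that. It remains true that the named models assume independence and that Aim 1 states its adjustment openly. An analyst who follows the Aim 2 text literally would fit the naive models.

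Third, Aim 2 is a within-arm predictor analysis with no stated alpha or selection rule. That limits the consequence but does not make the standard errors right.

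A reader might also infer that engagement counted up to month 12 is driven by weight loss, and that the plan therefore needs an analysis of month 6 engagement against weight change from month 6 to 12. The Aim 2 text sets no time window for the predictors, and its hypotheses speak of association. That analysis would leave out weight lost in the first six months and answer a different question. It is a matter of preference, not a correction.

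**Conclusion.** The point holds in limited form. As written, the Aim 2 regressions give standard errors that are too small for any predictor that clusters by provider, although the plan assumes such clustering in the outcome and handles it in Aim 1.

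With 8 to 9 providers of about 23 completers, true error at a nominal 5% is about 5 to 9% for mostly patient-level predictors, about 9 to 12% at a between-provider share of 0.5, and 13 to 19% only for a predictor constant within provider. With five clusters of 39 the figures are higher, up to about 25%.

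These figures rest on the plan's ICCs, an assumed two-sided 5% level, equal clusters and assumed predictor shares. In a multivariable model, the share that matters is that of the part of the predictor not explained by the other covariates. The figures are for the linear model. The logistic model has the same weakness, but its size was not computed. Where PACT counseling falls in the range is unknown.

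**What to change.** State in the Aim 2 Method that the linear and logistic regressions account for provider clustering, in one of two ways:
- a provider random intercept with small-sample degrees of freedom (for the linear model, Kenward-Roger or Satterthwaite); or
- a bias-corrected cluster-robust variance with a small-sample t reference. The plain sandwich is not enough with this few clusters.

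Name the variance method that will be used with the inverse-probability weights and confirm that it works with the chosen model. Report each predictor's between-provider share beside its estimate, so that readers can see how far clustering matters for it.

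The cost is a sentence or two of text and a small change in code; no new data are needed. Intervals become somewhat wider, mostly for predictors that differ between providers. The small-sample corrections named here were not simulated. A simple reference to t on 6 degrees of freedom with a random intercept was: it rejected only about 2% for predictors with a 10 to 20% share, so the degrees of freedom should be set per coefficient.
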